9.3 SEQUENCING OF NASAL SWABS FROM BREAKTHROUGH INFECTION

Self-collected nasal swabs will undergo whole genome sequencing for SARS-CoV-2. The distribution of clades and lineages identified from the BTI cases will summarised using frequencies and proportions. The distribution of SARS-CoV-2 clades/lineages over time be displayed graphically using a stacked bar chart (Monthly stacked bars with frequencies, with different segments for different clades/lineages).

9.4 SUPPLEMENTARY AND SENSITIVITY ANALYSES

The following supplementary and sensitivity analyses will be conducted. The supplementary analyses use alternative strategies for handling intercurrent events and thus target different estimands; the results will help to fully understand the impact of the intercurrent events and the strategies used to handle them. The sensitivity analyses target the same estimands and test the sensitivity of deviations from assumptions about missing data.⁴

Table 14. Supplementary and Sensitivity Analyses

Endpoints	MAIN ANALYSIS (Complete Case)		SUPPLEMENTARY ANALYSIS (for IcE Strategy)		SENSITIVITY ANALYSIS (for >5% missingness)
	Estimand	IcE & Strategy	Change to Estimand from Main Analysis	IcE & Strategy	
Primary immunological endpoint (seroresponse at Day-28)	Geometric mean ratio (GMR) of binding antibodies (IgG ELISA – Wuhan, Omicron BA.1 and Omicron BA.4/5) 28 days post-vaccination comparing the two vaccine groups (bivalent Moderna and Novavax) in adults 18 years or older who have received their third dose of COVID-19 vaccine at least six months previously, irrespective of SARS-CoV-2 infection.	SARS-CoV-2 infection: Treatment Policy	..., irrespective of SARS-CoV-2 infection ≤ 14 days post-booster, and in a hypothetical scenario in which there were no breakthrough infections on or after Day 15.	SARS-CoV-2 infection ≤ 14 days post-booster: Treatment Policy	Imagines a scenario in which breakthrough infections on or after Day 15 did not occur.
Day-28 Secondary immunological endpoints[#]	[Geometric mean ratio in [OUTCOME] OR Difference in Means of [OUTCOME]] [#] 28 days post-vaccination comparing the two vaccine groups (bivalent Moderna and Novavax), in adults 18 years or older who have received their third dose of COVID-19 vaccine at least six months previously, irrespective of SARS-CoV-2 infection.	SARS-CoV-2 infection: Treatment Policy	As above	As above	As above
Month-[6/12/18/24/30][#] Secondary immunological endpoints[#]	[Geometric mean ratio in [OUTCOME] OR Difference in Means of [OUTCOME]] [#] [6/12] [#] months post-vaccination comparing the two vaccine groups (bivalent Moderna and Novavax), in	SARS-CoV-2 infection: Treatment Policy	..., irrespective of SARS-CoV-2 infection ≤ 14 days post-booster or receipt of a 5 th dose (self-initiated), and in a	SARS-CoV-2 infection ≤ 14 days post-booster:	As above

	adults 18 years or older who have received their third dose of COVID-19 vaccine at least six months previously, irrespective of breakthrough infections or receipt of a 5th dose (self-initiated).	Self-initiated 5 th dose: Treatment Policy	hypothetical scenario in which there were no breakthrough infections on or after Day 15	Treatment Policy Receipt of 5 th dose (self-initiated): Treatment Policy
	Geometric mean ratio in [OUTCOME] OR Difference in Means of [OUTCOME] [#] [6/12] ^Δ months post-vaccination comparing the two vaccine groups (bivalent Moderna and Novavax), in adults 18 years or older who have received their third dose of COVID-19 vaccine at least six months previously, irrespective of breakthrough infections or receipt of a 5th dose (self-initiated).	SARS-CoV-2 infection: Treatment Policy Self-initiated 5 th dose: Treatment Policy	... , irrespective of SARS-CoV-2 infection, and in a hypothetical scenario in which no participants received a self-initiated 5 th dose.	SARS-CoV-2 infection: Treatment Policy Receipt of 5 th dose (self-initiated): Hypothetical [§]
Month- [6/12/18/24/30]^Δ Secondary immunological endpoints[#]	Geometric mean ratio in [OUTCOME] OR Difference in Means of [OUTCOME] [#] [6/12] ^Δ months post-vaccination comparing the two vaccine groups (bivalent Moderna and Novavax), in adults 18 years or older who have received their third dose of COVID-19 vaccine at least six months previously, irrespective of breakthrough infections or receipt of a 5th dose (self-initiated).	SARS-CoV-2 infection: Treatment Policy Self-initiated 5 th dose: Treatment Policy	... , irrespective of SARS-CoV-2 infection \leq 14 days post-booster, and in a hypothetical scenario in which: - there were no breakthrough infections on or after Day 15, AND; - no participants received a self-initiated 5 th dose.	SARS-CoV-2 infection \leq 14 days post-booster: Treatment Policy Receipt of 5 th dose (self-
				initiated 5 th dose.

			initiated): Hypothetical ⁶	
--	--	--	--	--

⁶This row is generic for all immunological endpoints at the specified timepoint (see Table 8). This row is generic for the Month-6 and Month-12 timepoints. ⁶Under the hypothetical strategy, outcome values experienced after the specified intercurrent events will be set to missing and multiple imputation will be used to calculate the estimate including these participants. [The parts of the Estimands and intercurrent event strategies that are being modified in each supplementary analysis are highlighted by blue text.](#)

9.4.1 Implementation of the Hypothetical Strategy

Under the hypothetical strategy, outcome values experienced after the specified intercurrent events will be set to missing and multiple imputation will be used to calculate the estimate including these participants. Multiple imputation for analyses under the hypothetical strategy will be carried out using the same imputation procedure used to handle missing data (see Section 4.10). Imputation will be done separately by trial arm. For Month-6, Month-12, Month-18, Month-24 endpoints and Month-30 endpoints, levels of the outcome variable at previous blood draws will also be included in the imputation model.

9.5 SUBGROUP ANALYSES AND TESTS FOR INTERACTION

Analyses for all endpoints will be conducted amongst all strata combined. Primary analyses will combine data from participants receiving the Moderna BA.1 and Moderna BA.4/5 vaccines. Subgroup analyses stratified by the age strata (<50 and ≥50 years) will also be conducted for the immunological endpoints and breakthrough infection secondary endpoints. Subgroup analyses will also be performed by Moderna vaccine timing (Moderna BA.1 period vs Moderna BA.4/5 period) for immunological endpoints. Tests of interaction will be done by fitting a model with an interaction parameter between study arm and the age strata.

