4 TRIAL DESIGN

4.1 Study design

This clinical trial will be a blinded, two-arm randomised study to determine the safety, reactogenicity and immunogenicity of a fourth dose of SARS-CoV-2 vaccines in Australia in adults 18 years or older who have received their third dose of COVID-19 vaccine, at least six months previously. A separate non-randomised control arm will be enrolled for comparison. The groups are described below. The trial intervention will be a single booster dose of vaccine: -

Group	Vaccine given
Group A – (Moderna) 225 participants	Bivalent Moderna (mRNA-1273.214) (Ancestral SARS-CoV-2 25 μ g + Omicron Variant (B.1.1.529) 25 μ g). Replaced by Bivalent Moderna (mRNA-1273.222) (Ancestral SARS-CoV-2 25 μ g + Omicron Variant (BA.4-5) 25 μ g) when introduced.
Group B – (Novavax) 225 participants	Novavax (5 μ g of SARS-CoV-2 spike protein adjuvanted with 50 μ g of Matrix-M)
Group C – (Control group) 150 participants	No vaccine given

We will aim to enrol approximately 225 individuals in each vaccine group and 150 individuals in the control group. This will ensure sufficient representation of participants aged < 50 and \geq 50 years receiving the newer Moderna BA.4-5 vaccine.

The participants and those evaluating reactogenicity will be blinded to the vaccine allocation for the first seven days following vaccination until details are entered in the Australian Immunisation Register (AIR). After that, participants will be aware of their investigational product allocation. Immunologists and laboratory staff will remain blinded to the investigational product allocation.

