11 STATISTICAL METHODS

11.1 Sample Size Estimation

Sample size calculations were performed using nQuery 8 software and methods described by Van Belle, et al. 1993 (20). Precision-based sample size calculations were performed based on the reactogenicity outcomes. Assuming the percentage of participants reporting local or systemic reactions is 50%, 100 participants will produce a confidence interval that is 9.8 percentage points from the observed percentage. For immunogenicity, sample size calculations were based on comparing day 28 post-booster geometric mean concentrations of IgG antibodies between vaccine arms. We assumed the coefficient of variation (standard deviation/mean) of the post-booster antibody concentrations would be 1.15 (based on data from Munro, et al. 2021 (8), but increased to be conservative). Even though previous studies demonstrated a geometric mean ratio (GMR) of up to 4 between the study vaccine groups, we considered a clinically important difference between groups to be a GMR of >1.4. Based on these assumptions the study will need to recruit 160 participants in each vaccine group overall to achieve 90% of power at two-sided 0.05 significance level. Allowing for ~20% loss to follow-up the sample size in each arm was expanded to 200. To ensure age representation (<50 and ≥50) in the second Moderna bivalent group (BA.4-5) numbers were increased in the younger age group.

We are confident that the sample size is sufficient as it is likely that the GMR difference will be higher than expected and the loss to follow-up lower than anticipated.

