3.1 STUDY DESIGN

This clinical trial is a blinded, two-arm randomised study to determine the safety, reactogenicity and immunogenicity of a fourth dose of SARS-CoV-2 vaccines in Australia in adults 18 years or older who have received their third dose of COVID-19 vaccine, at least six months previously. A separate non-randomised control arm will be enrolled for comparison. The groups are described below. The trial intervention will be a single booster dose of vaccine:

Group	Vaccine given	N
Group A – (Moderna)	Bivalent Moderna (mRNA-1273.214) (Ancestral SARS-CoV-2 25µg + Omicron Variant (B.1.1.529) 25µg). Replaced by Bivalent Moderna (mRNA-1273.222) (Ancestral SARS-CoV-2 25µg + Omicron Variant (BA.4-5) 25µg) when introduced.	225
Group B – (Novavax)	Novavax (5µg of SARS-CoV-2 spike protein adjuvanted with 50µg of Matrix-M)	225
Group C – (Control group)	No vaccine given	150

Note: Unless otherwise stated, all analyses of the Bivalent Moderna vaccine arm (Group A) will comprise data from the Moderna BA.1 and Moderna BA.4-5 groups combined.

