3.2 STUDY GROUPS AND RANDOMISATION

The two vaccine groups (Groups A and B) will be randomised 1:1 to one of two interventions (bivalent Omicron-specific Moderna and Novavax) stratified by age (<50 and ≥50 years). An independent statistician from the Melbourne Children's Trial Centre at the Murdoch Children's Research Institute will provide a secure, password-protected web-based randomisation schedule. Blocked randomisation will be used with random blocks of permuted length.

50% of participants from each vaccine group will be included in the cell-mediated immunity (CMI) subgroup analysis. We will ensure that the age strata (<50 and ≥50 years) are equally represented in the CMI vaccine groups.

The control group will not be randomised and will be recruited from participants <60 years of age who indicate that they are not planning to receive a fourth vaccine dose at the time of recruitment. Controls will be recruited into proportional pre-defined age bands (18-29 years, 30-49 years, 50-59 years).

Table 1. Study groups and strata

Group	Age group	Booster vaccine	Dose given	Number
Group A	<50 years	Bivalent Moderna BA.1	50µg	75
	<50 years	Bivalent Moderna BA.4-5	50µg	75
	≥50 years	Bivalent Moderna BA.4-5	50µg	75
Group B	<50 years	Novavax	50µg	150
	≥50 years	Novavax	50µg	75
Group C	<60 years	No vaccine	-	150

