4.5 MULTIPLICITY ADJUSTMENT

This trial will evaluate multiple outcomes, including multiple (sub)variants for the immunogenicity outcomes (Wuhan, Omicron BA.1, Omicron BA.4/5, Omicron JN.1). To avoid multiple primary outcomes, this SAP has specified binding antibody levels (IgG) for the Wuhan strain at Day-28 as the primary immunological endpoint. For group comparisons, treatment effects with 95% confidence intervals will be presented. Results will be interpreted based on the magnitude of the treatment effects. No multiplicity adjustments have been planned.

Secondary outcome results will be interpreted precisely (including the timepoint and the specific outcome) so that the per-comparison-wise error rate is not increased and adjustment for multiplicity is not required.³

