6.2 IMMUNOGENICITY OUTCOME VARIABLES

Table 3 lists the immunogenicity outcome variables including the units, and participant subsets in which the outcomes are measured. There may be additional immunogenicity outcome variables (e.g. for additional variants) that may become available after this SAP is written.

Table 3. Description of immunogenicity outcome variables, including units and subsets in which they are measured

	Outcome	Subset	Units
Main study	Binding antibody (IgG) (Euroimmun Wuhan)	All	BAU/ml
	Binding antibody (IgG) (Euroimmun Omicron BA.1)	All	RU/ml
	Binding antibody (IgG) (In-house assay Omicron BA.4/5)	All	EU/ml
	Binding antibody (IgG) (In-house assay Omicron JN.1)	All	EU/ml
	Binding antibody (IgG) (N-Protein)	All	EU/ml
	Functional antibody (C-PASS assay - sVNT Wuhan)	All	U/mL
	Functional antibody (C-PASS assay - sVNT Omicron BA.1)	All	U/mL
	Functional antibody (C-PASS assay - sVNT Omicron BA.4/5)	All	U/mL
	Neutralising antibody (Wuhan)	20% of samples	NT50
CMI sub-study	Neutralising antibody (variant of concern)*	20% of samples	NT50
	IFN γ	50% of participants	IU/ml

[^]Baseline measurements are also taken at Day 0

* Variants of concern to be confirmed

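### On the planned cells, the SAP's arm-by-age test on the pooled Moderna arm combines age modification with half of any BA.1 versus BA.4-5 product/period difference, and no planned estimate separates the two

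*SAP*

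**What the plan says.** SAP 9.5 pools the two Moderna products for the primary analyses and plans subgroup analyses by age stratum (under 50, and 50 or over). It names one interaction model: "Tests of interaction will be done by fitting a model with an interaction parameter between study arm and the age strata". It adds: "Subgroup analyses will also be performed by Moderna vaccine timing (Moderna BA.1 period vs Moderna BA.4/5 period) for immunological endpoints". The timing subgroup is not crossed with age, and no interaction term is named for it. SAP 3.1 gives the general rule that, unless otherwise stated, "all analyses of the Bivalent Moderna vaccine arm (Group A) will comprise data from the Moderna BA.1 and Moderna BA.4-5 groups combined".

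SAP 3.2 Table 1 and the allocation table in Protocol 6.1 give the same planned cells. The only row labelled "Bivalent Moderna BA.1" is for participants under 50.

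| Planned cell | Under 50 | 50 or over |
|---|---|---|
| Moderna BA.1 | 75 | no row |
| Moderna BA.4-5 | 75 | 75 |
| Novavax | 150 | 75 |

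The adjustment set in SAP 7.2 Table 6 is age group, baseline level, first booster vaccine and time since first booster. It has no product or period term.

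The sponsor enlarged the younger group on purpose. Protocol 4.1 wants both age groups represented among those "years receiving the newer Moderna BA.4-5 vaccine", and Protocol 11.1 says that "in the second Moderna bivalent group (BA.4-5) numbers were increased in the younger age group".

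**The concern.** Product and calendar period are tied to age by design. Half of the younger Moderna recipients are planned to receive BA.1 and none of the older ones. The younger arm effect therefore averages two product periods, while the older arm effect comes from one. Any difference between the periods in the Moderna/Novavax ratio enters the arm-by-age coefficient and could be reported as an age effect. With the opposite sign, it could mask a real one.

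This is more plausible for the Omicron endpoints (IgG BA.1, BA.4/5 and JN.1; sVNT BA.1 and BA.4/5; SAP 8.1 Table 8) than for the Wuhan primary. Protocol 5.2 gives both products the same 25 µg ancestral component, and only the Omicron component differs.

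The enlarged younger group provides a balanced set, 75 against 75 in each age stratum within the BA.4/5 period, but no planned age contrast uses it.

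**Working it through.** **Inputs.** The cells are those in SAP 3.2 Table 1. The coefficient of variation is 1.15, the target GMR 1.4, alpha 0.05 two-sided and loss about 20% (SAP 3.5). Novavax is not tabulated by period. I assume 75 and 75 in the under-50s, as concurrent 1:1 randomisation implies. No precision gain from covariates is assumed.

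**The plan's own figure first.** The log-scale variance is σ² = ln(1 + 1.15²) = 0.8426, so σ = 0.918. Then n = 2 × (1.960 + 1.282)² × 0.8426 / (ln 1.4)² gives 157 per arm (158 with the t distribution), against the stated 160. Dividing 160 by 0.8 gives the stated 200. The documents give no figure for the interaction test.

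**What the coefficient estimates.** On the log scale, let θ be the Moderna versus Novavax effect in under-50s in the BA.4/5 period. Let δ be the true age modification in that period. Let r be the BA.4/5-period GMR divided by the BA.1-period GMR in under-50s.

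- Effect at 50 or over: θ + δ.
- Effect under 50: ½(θ − ln r) + ½θ = θ − ½ ln r.
- Arm-by-age coefficient: the difference, **δ + ½ ln r**.

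Least squares on the planned cells gives weight 1.0 on δ and 0.5 on ln r. Adding period as a main effect alone leaves the 0.5. Adding period and arm-by-period takes it to 0. More generally, with concurrent Novavax, the weight is the BA.1 share among younger Moderna recipients minus the share among older ones.

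**The timing subgroup has the mirror problem.** The BA.1-period effect is θ − ln r. The BA.4/5-period effect, with half its participants aged 50 or over, is θ + ½δ. They differ by ln r + ½δ. With no product effect, a true age ratio of 1.2 or 1.4 would make the two period GMRs differ by a factor of 1.10 or 1.18.

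**Size when δ = 0.** The standard error (SE) of the planned term is √(2 × 0.8426/150 + 2 × 0.8426/75) = 0.184, or 0.205 after 20% loss. Rejection is P(|Z + ½ ln r / SE| > 1.96).

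| Assumed r | Spurious age ratio (√r) | Rejection, full numbers | Rejection, 20% loss |
|---|---|---|---|
| 1.1 | 1.05 | 5.8% | 5.6% |
| 1.2 | 1.10 | 7.9% | 7.3% |
| 1.4 | 1.18 | 15.0% | 13.0% |

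If 20% of older Moderna recipients in fact received BA.1, the weight falls to 0.3. Then r = 1.2 and 1.4 give 1.06 and 1.11, with rejection of 6.0% and 8.5%. At 50% the extra term vanishes.

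**Companion estimate.** Arm-by-age within the BA.4/5 period has weight 0 on ln r and SE √(4 × 0.8426/75) = 0.212 (0.237 after loss). Power at an age ratio of 1.4 is 35.5%, against 44.9% for the planned term (29.4% against 37.4% after loss).

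**The case against.** Nothing planned is wrong as an estimate of what it describes. SAP 3.1 and 9.5 say openly that the Moderna arm pools both products, and no section says that the interaction will be read as age modification independent of product. This stands: the issue is interpretation of a secondary test.

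The size rests wholly on an assumed r. At r = 1.2 the shift is 0.091, half of one SE, and the 95% CI of the planned term already spans a factor of about 1.43 either way. This also stands.

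The companion can be approximated from planned output. The log GMR for BA.4-5 under 50 is twice the under-50 log GMR minus the BA.1-period log GMR. Its variance is 4 × 0.01123 − 0.02247 = 0.0225, the same as the direct variance 2 × 0.8426/75. A reader might infer that the information is lost without new wording. It is not, and what is gained is a direct, covariate-adjusted estimate that is actually reported.

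A reader might also infer that the interaction test is invalid or the primary Day-28 GMR biased. The documents support neither. The pooled contrast is randomised, and each within-subgroup ratio stands for the mix delivered, given concurrent Novavax.

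SAP 4.5 says "Results will be interpreted based on the magnitude of the treatment effects". That makes a shifted estimate relevant even without significance, but the sentence concerns group comparisons and does not mention interaction ratios, so little weight can be put on it.

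Finally, the cells are targets. The Protocol synopsis, Protocol 4.3 and SAP 3.4 promise an even or equitable age distribution across the Moderna transition. That conflicts with the empty BA.1 cell at 50 or over, so the realised mixing may be smaller.

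**Conclusion.** The concern holds as a minor point of interpretation. On the planned cells the arm-by-age term is exactly age modification plus half the log product/period difference, and neither the planned covariates nor the timing subgroup separates the two. The structure is certain given those cells. The size is not: spurious ratios of 1.05 to 1.18 correspond to assumed r of 1.1 to 1.4, with rejection between about 6% and 15%.

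The one-half depends on the 75:75 split among younger Moderna recipients, on no BA.1 at 50 or over, and on Novavax dividing by period in the same way. With a 90:60 Novavax split the weight stays 0.5, but a calendar effect common to both arms also enters, with weight −0.1.

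Two stronger conclusions would not be justified. An age interaction, if found, is not thereby shown to be a product artefact. Nor should the BA.4/5-only estimate replace the planned one: under the same assumptions its mean squared error is the larger until r exceeds about 1.24 (shift √(0.0449 − 0.0337) = 0.106, and e^(2 × 0.106) = 1.24).

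**What to change.** In SAP 9.5:

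1. Keep the planned arm-by-age test. State that it describes the pooled Moderna arm and, on the planned cells, carries half of any product/period difference.
2. For the endpoints measured in all participants (IgG and sVNT in SAP 6.2 Table 3, for example "Binding antibody (IgG) (In-house assay Omicron BA.4/5)"), add a sensitivity estimate with 95% CI. This is arm-by-age among participants randomised in the BA.4/5 period or, equivalently on the planned cells, the arm-by-age term from a model with age, period, arm-by-age and arm-by-period.
3. Set no rule that the two estimates must agree before age modification is claimed. Their difference has SE 0.106, so a gap of up to about 1.23-fold is compatible with chance, and conditioning on the noisier estimate could suppress a real effect.
4. Where the BA.1-period and BA.4/5-period GMRs are set side by side, also give the comparison within under-50s, noting that it reflects calendar time as well as product.
5. Tabulate actual age-by-product counts, and reconcile the cell tables with the text on age distribution across the transition.

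The cost is a few lines of SAP text and no new data. The price is precision: SE 0.212 against 0.184, and power at a ratio of 1.4 of about 35% against 45%. The companion is not practical in the 20% neutralisation subset (about 15 per cell, SE about 0.47 if the same coefficient of variation held). SAP 1.2 and 4.8 show Day 28 covered by an earlier plan and analyses triggered visit by visit, so the companion should be labelled post hoc for every timepoint already analysed, not only Day 28.

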9.6 ANALYSIS OF SAFETY ENDPOINTS

Analyses for all safety endpoints will be amongst all randomised participants according to the trial vaccine received (the “Safety Population”). Recurrent events in the same individual will be counted as a single event (using information from the most severe occurrence); all recurrences will be included in the line list of all adverse events. Population measures for all safety endpoints will be reported separately by study group. Analyses of all safety endpoints will be descriptive only. Missing data on severity, onset, SOC, causality, SAE outcome, and SAE expectedness will be described by study group.

In addition, a list of all adverse events will be provided by trial vaccine including the following parameters:

- the patient identifier
- age
- sex
- adverse event (reported term, lower-level term, and SOC)
- day of onset (from Day 0)
- duration (in days)
- severity grade
- seriousness (serious/non-serious)
- special interest (yes/no)
- expectedness (yes/no)
- action taken
- outcome (Resolved, Resolved with sequelae, Ongoing, Fatal and Unknown)
- causality assessment/relatedness (*noting ‘adverse reactions’ and ‘serious adverse reactions’*)
- concomitant medication at baseline
- concomitant medication during study (prior to event)
- concomitant medication in response to event
- comorbidities at baseline
- brief narrative (SAEs only)

